6.20.1.2.4. Differential Item Functioning (DIF)

Differential Item Functioning (DIF) analysis refers to procedures that assess whether items on an instrument perform in the same manner for various groups of patients. Differential Item Functioning procedures typically control for overall between-group differences on a criterion, usually the scores of the instrument (Zumbo 1999). In this study, DIF analysis will be conducted on the GPSS items score, GPSIS subscale and SFQ item to clarify whether the items perform differently by sex (male vs. female), while controlling for their scale scores. The scale scores as

determined on the basis of the factor analysis and Rasch model analysis will be used in the DIF analysis. Sample sizes of the subgroups will be checked prior to conducting DIF. Differential Item Functioning analysis will only be performed when sample sizes are sufficient (that is, ≥ 50).

Ordinal logistic regression models will be used in the DIF analyses. Differential Item Functioning will be conducted for each item. Each model will have the scale item score as the dependent variable, the grouping variable “sex” as the factor, the Rasch logit scale score as the covariate, and the interaction term for “sex” by Rasch logit scale score. The grouping variable “sex” is called a bias factor. The Rasch logit scale score is a derived score of the Rasch based on the factor analysis model and will be used as the measure of the underlying construct of severity for the DIF analysis. Ideally, only the underlying construct influences the way participants respond to the items, and the bias factor does not influence the dependent variable. However, if an item exhibits DIF, then the bias factor, in addition to the latent construct, also affects the way the participants respond to the items.

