GPSS	
The Genital Psoriasis Symptoms Scale (GPSS) is a patient-administered assessment of 8 symptoms: itch, pain, discomfort, stinging, burning, redness, scaling, and cracking. Respondents are asked to answer the questions based on their psoriasis symptoms in the respective genital areas.
 
The overall severity for each individual symptom from patient's genital psoriasis is indicated by selecting the number from an NRS of 0 to 10 that best describes the worst level of each symptom in the genital area in the past 24 hours, where 0 (= no severity) and 10 (worst imaginable severity).
 
The symptom severity scores, ranging from 0 to 10, are the values of the selected numbers indicated by the patient on the instrument's horizontal scale. Each of the 8 individual items will receive a score of 0 to 10 and will be reported as item scores for itch, pain, discomfort, stinging, burning, redness, scaling, and cracking. In addition, a total score ranging from 0 (no genital psoriasis symptoms) to 80 (worst imaginable genital psoriasis symptoms) will be reported.
	GPSS total score	
The GPSS total score will be calculated by summing the individual item scores as follows: GPSS = itch NRS + pain NRS + discomfort NRS + stinging NRS + burning NRS + redness NRS + scaling NRS + cracking NRS
 
The GPSS total score at Week 12 (Visit 7) is the average of at least 4 non-missing scores of the last 7 consecutive days. The 7-day window ends on the date of Visit 7 when the data is collected on site, and on or after the date of previous visit.
 
The GPSS total score at Week 2 (Visit 4), Week 4 (Visit 5), and Week 8 (Visit 6), is the average of at least 4 non-missing scores of the last 7 consecutive days before the date of current visit, and on or after the date of previous visit.
 
The GPSS total score at Week 1 (Visit 3), the 7-day window is before the date of Visit 3, and on or after the date of the first injection.
 
Note 1: For derivations of post-baseline visit scores, when there are less than 4 non-missing scores in the 7-day window, the window will be extended one day at a time, up to 10 days, until 4 non-missing scores are found, but the window will not be extended beyond the date of previous visit. If at least 4 non-missing scores are still not found, the visit score will be designated as missing.
 
Note 2: When 7-day duration is not present between visits, the visit score will be the average of at least 4
	If any item score is missing, the GPSS total score will be missing.

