	
sexually active in the past week. Item 3 asks the patient about his/her worsening of genital psoriasis symptoms following sexual activity.
 
Total score is not calculated for the GPSIS.
		
examined, and defined as the last non-missing subscale score collected in the calendar week.
 
The calendar week is defined as follows: Calendar Week 1 is from study day 1 to 7; Calendar Week 2 is from study day 8 to 14; ... Calendar Week 11 is from study day 70 to 77; Calendar Week 12 is from study day 78 to the date of Visit 7.
 
Note that study day 1 is the date of the first injection during the Blinded Treatment Period.
	
		
GPSIS Sexual Activity Avoidance Subscale score of 1 or 2
	
The subscale score is assessed as 1 or 2
	
Missing if the subscale score is missing

Measure	Description	Variable	Derivation	Imputation Approach if Components are Missing
		GPSIS Impact of Sexual Activity on Genital Psoriasis Symptoms Subscale	
Those patients who report as being sexually active (i.e. with a score of 0 on Item 1) on the GPSIS item 1 are given the opportunity to respond to item 3. Item 3 asks the patient to select a response to reflect the level (degree) of worsening of genital psoriasis symptoms following sexual activity as described below: 1 = very low or not at all 2 = low 3 = moderate 4 = high 5 = very high
 
The Impact Subscale Score, at each post-baseline visit in the Blinded Treatment Period and Open-Label Treatment Period, is derived in the same manner as Sexual Activity Avoidance Subscale Score.
 
The Impact Subscale Score, at each calendar week in the Blinded Treatment Period, is derived in the same manner as Sexual Activity Avoidance Subscale Score.
	
The Impact of Sexual Activity on Genital Psoriasis Symptoms Subscale score is missing if:
 
Item 1 is missing; or Item 1 is answered as “Yes” (score of 0) but Item 3 is missing.
 
Note: Patients, who report as not being sexually active due to genital psoriasis or other reasons (i.e. with a score of 1 or 2 on Item 1), are considered to be “Not Applicable” for this subscale, but will NOT be considered as missing.

Measure	Description	Variable	Derivation	Imputation Approach if Components are Missing
		GPSIS Impact of Sexual Activity on Genital Psoriasis Symptoms Subscale score of 1 or 2	The subscale score is assessed as 1 or 2.	Missing if the subscale score is missing

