SFQ	
The SFQ is a patient reported outcome measure to evaluate the impact of genital psoriasis symptoms on sexual frequency. It consists of 2 items that assess the impact of genital psoriasis symptoms on the frequency of sexual activity. Respondents are asked to answer the questions based on their psoriasis symptoms in the genital area.
 
Item 1 asks how many times the patient engaged in sexual activity in the past week with response options of: 2 = none/zero 1 = once 0 = two or more
 
Item 2 assesses how often genital psoriasis symptoms limited the frequency of sexual activity with the following response options: 0 = never 1 = rarely 2 = sometimes 3 = often 4 = always
	SFQ Item 1	
Item 1 score as reported in the weekly e-diaries. The score ranges from 0 to 2.
 
Item 1 Score at Week 12 (Visit 7) is the score collected at Visit 7 on site.
 
Item 1 Score at Week 2 (Visit 4), Week 4 (Visit 5), and Week 8 (Visit 6) is defined as the last non-missing score collected before the date of the visit, and on or after the date of previous visit.
 
Item 1 Score is the lasting non-missing score before the date of Visit 3 and on or after the date of the first injection.
 
For the visit beyond Week 12 (Visit 7), the score is as being collected at that visit on site.
	Missing if the item 1 score is missing
		SFQ Item 2	
Item 2 score as reported in the weekly e-diaries. The score ranges from 0 to 4.
 
Item 2 Score, at each post-baseline visit in the Blinded Treatment Period and Open-Label Treatment Period, is derived in the same manner as Item 1 Score.
	Missing if the item 2 score is missing

Measure	Description	Variable	Derivation	Imputation Approach if Components are Missing
	The individual item scores of the SFQ are reported separately. No total score is calculated for the SFQ.		
For exploratory analyses, Item 2 Score at each calendar week is examined, and defined as the last non-missing subscale score collected in the calendar week.
 
The calendar week is defined as follows: Calendar Week 1 is from study day 1 to 7; Calendar Week 2 is from study day 8 to 14; ... Calendar Week 11 is from study day 70 to 77; Calendar Week 12 is from study day 78 to the date of Visit 7.
 
Note that study day 1 is the date of the first injection during the Blinded Treatment Period.
	
		SFQ Item 2 Score of 0 or 1	Item 2 score is assessed as 0 or 1.	Missing if the item 2 score is missing

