6.20.1.2.3. Factor Analysis

Exploratory Factor Analysis (EFA) will be conducted using baseline GPSS data. Exploratory Factor Analysis will be used to uncover the underlying factor structure of the measures. Screen plots and corresponding eigenvalues will be examined to empirically inform the number of factors underlying the GPSS items. Factor loadings, standardized mean square residual (SRMR), and root mean square error of approximation (RMSEA) will be examined to evaluate model goodness-of-fit. It is recommended that the SRMR and RMSEA values be less than 0.8. Orthogonal and/or oblique rotation (Yates 1987) will be used in the analysis since the factors are expected to be correlated. An approximate simple structure will be the criterion for accepting a factor solution; oblique rotation will be conducted and correlations between factors will be reported, if necessary.

The GPSS includes multiple items and these analyses will evaluate the performance of each item in order to identify items that may be redundant or perform poorly. Items with low standardized loading <0.40 , or items with similar factor loadings across multiple domains indicate items that may be candidates for removal. Interpretability of factors and clinical judgment will also be considered in the selection of the final model.

Confirmatory factor analysis (CFA) will be conducted using Week 1 data to evaluate the conceptual framework for the GPSS. It is hypothesized that the GPSS will yield a one factor solution similar to other symptom measures for plaque psoriasis (Revicki et al. 2014). Confirmatory factor analysis will be conducted to model factor loadings based on the final conceptual model derived in the EFA analyses.

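### The planned test for differential item functioning by sex has no usable matching score for the GPSIS subscales and the SFQ item

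*SAP*

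**What the plan says.** SAP 6.20.1.2.4 sets the scope: "DIF analysis will be conducted on the GPSS items score, GPSIS subscale and SFQ item to clarify whether the items perform differently by sex", with the condition "while controlling for their scale scores". One ordinal logistic model serves every item. The item score is the outcome and sex is the factor, with "the Rasch logit scale score as the covariate, and the interaction term for" sex by that score. On where the covariate comes from, the section says: "The Rasch logit scale score is a derived score of the Rasch based on the factor analysis model". Its only stated condition for running the analysis is subgroup size, at least 50.

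The factor analysis it relies on is in SAP 6.20.1.2.3: "Exploratory Factor Analysis (EFA) will be conducted using baseline GPSS data". The confirmatory step there is also for the GPSS.

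The scoring rules are in SAP 6.10, Table RHBQ.6.4, and protocol 8.1.2.2:

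- GPSS: "Each of the 8 individual items will receive a score of 0 to 10", and the items sum to a total of 0 to 80.
- GPSIS: "Total score is not calculated for the GPSIS". Protocol 8.1.2.2.2 builds the Impact subscale from Item 3 alone. The Avoidance subscale merges Items 1 and 2 by rule into one score from 1 to 5.
- SFQ: "No total score is calculated for the SFQ". Its two items are reported separately.

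**The concern.** A DIF model asks whether two groups at the same level of the underlying trait answer an item differently. The matching score stands in for the trait, so it must carry information beyond the item under test. The GPSS can supply such a score because it has eight items. The GPSIS subscales and the SFQ items cannot, on the scoring rules in the same SAP.

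What is at stake is the psychometric summary promised in SAP 6.20.1.1. If the section is followed literally, two of its three named targets have either no defined covariate or a degenerate model. An absence of DIF recorded from such a fit would be a statement about measurement validity with nothing behind it.

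**Working it through.** The documents give no power or sample-size figure for DIF, so there is no stated figure to reproduce. The check has a structural part and a simulation.

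**1. Which targets have a scale score distinct from the item?**

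| Target | Content | Total | In the factor analysis | Distinct matching score |
|---|---|---|---|---|
| GPSS item | 1 of 8 items, each 0 to 10 | 0 to 80 | yes | yes |
| GPSIS Impact | Item 3 only | none | no | no |
| GPSIS Avoidance | Items 1 and 2 merged, 1 to 5 | none | no | no |
| SFQ item | reported on its own | none | no | no |

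Testing Item 2 inside the Avoidance subscale does not help. Only sexually active patients answer it, and for them the subscale score is the Item 2 response. The SAP treats the measures the same way elsewhere: internal consistency is planned for the GPSS only (6.20.1.2.5), and the test-retest section calls most of the measures single-item scales (6.20.1.2.5.2).

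Two strict readings remain for GPSIS and SFQ. Either the Rasch covariate does not exist for them, because its parent model covers the GPSS alone, or their scale score is the item itself.

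**2. What happens if the item is matched on itself?**

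The planned model, for item Y, sex s and matching score m, is

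logit P(Y ≤ k) = θ_k − (β·m + γ·s + δ·m·s).

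A Rasch logit derived from a single item is at best a one-to-one, increasing transform of that item, so each level of m corresponds to one level of Y. Place each θ_k between adjacent values of β·m and let β grow. Every fitted probability for the observed category tends to 1 and the log-likelihood tends to 0, its maximum. This already happens with γ = δ = 0, so the likelihood-ratio statistic for sex plus interaction is 2 × (0 − 0) = 0 whatever the true sex difference.

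**3. Simulation.**

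From the SAP: N = 146 and the proportional-odds model above. Assumed, because the documents do not give them: 35% women; a standard normal trait with slope 1.7 on the logit scale; a five-level item; a uniform sex shift of 0, 1 or 2 logits. The test is the 2-degree-of-freedom likelihood-ratio test at 0.05, with critical value −2 ln(0.05) = 5.99, and there were 100 runs per cell.

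| Matching score | Shift 0 | Shift 1 | Shift 2 |
|---|---|---|---|
| The item itself | 0% | 0% | 0% |
| Item plus one companion item | 4% | 43% | 87% |
| Independent 8-item score | 6% | 69% | 99% |

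In the first row the likelihood-ratio statistic never exceeded 0.0001, and the model without sex already fitted perfectly. With 100 runs, the simulation standard error at 69% is √(0.69 × 0.31 / 100) = 4.6 percentage points. The last row shows what a valid match can do. It is not the power of the planned GPSS analysis, where the matching score would include the tested item.

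**4. The sample-size condition does not screen this out.** If at least 50 means 50 of each sex, the smaller sex must make up 50/146 = 34% of patients. The documents do not give the sex mix. Meeting that condition would leave the matching problem untouched.

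**The case against.** The best case for the plan is that self-matching is nowhere written. SAP 6.20.1.2.4 calls its one covariate a measure of underlying severity derived from the factor analysis, which is a GPSS analysis. It could therefore mean a GPSS-based score for all three instruments, and for GPSIS and SFQ that would be an external match. For the SFQ, one could also argue that the statement about totals governs reported efficacy scores and does not forbid a two-item matching score inside a psychometric model. The simulation shows that such a score would have some power (43% and 87%).

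Part of this stands: the text is ambiguous, and it would go too far to say that the SAP instructs the analyst to match an item on itself. But a GPSS match conflicts with the requirement to control for each measure's own scale score, a summed SFQ score is one the SAP says is not calculated, and neither defence rescues the one-item Impact subscale.

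A reader might also point to the words in 6.20.1.1 that analyses are done where possible. The list there does not name DIF, whereas 6.20.1.2.4 names GPSIS and SFQ outright.

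Two stronger inferences should be resisted. One is that the plan would report an absence of DIF whatever the data. Complete separation more often shows as a failed or degenerate fit, and nothing in the SAP tells the analyst to report that as a negative finding. The other is that Major Secondary #3, which uses SFQ Item 2, is weakened. Its definition, population and test are fixed in SAP 6.4 and 6.11, and no DIF result feeds into them.

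**Conclusion.** The point holds for GPSIS and SFQ and not for the GPSS items, where the approach is workable. As written, the covariate for GPSIS and SFQ is either undefined or the item itself. In the first case the model cannot be run. In the second it separates completely and has no power, by algebra and in simulation (0% rejection at shifts of 0, 1 and 2 logits). Either way it yields no valid evidence for or against a sex difference in these measures.

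The algebra rests only on the matching score being a one-to-one function of the item. The contrast rates depend on the assumed sex mix, slope and shifts, and only illustrate that the obstacle is the matching variable and not the sample size. The consequence is small: the analysis is exploratory, and no primary or gated secondary test changes.

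**What to change.** In SAP 6.20.1.2.4, limit the Rasch-matched DIF model to the eight GPSS items, delete GPSIS and SFQ from its scope, and state that no conclusion about DIF by sex will be drawn for them. The subgroup-size condition can stay.

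If a sex comparison is still wanted for SFQ Item 2 or the GPSIS subscales, use baseline PatGA-Genital as the matching covariate in the same ordinal model. It is collected at Week 0 (protocol Appendix 2), and the SAP already lists it as a convergent measure for both (6.20.1.2.5.3.1). Baseline sPGA of Genitalia is a poor choice because inclusion criterion [4] requires a score of 3 or more, leaving only levels 3 to 5. Report the result as a sex difference conditional on patient-rated severity, not as item bias. Severity is a different construct from sexual avoidance or limitation, so a real sex difference in impact would otherwise be read as a faulty item.

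The cost is SAP wording only, with no new data and no change to any confirmatory analysis.

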6.20.1.2.5. Psychometric Analyses

Following the examination of the distributional characteristics of measures, the following psychometric properties of the instruments will be evaluated: internal consistency (GPSS only), test-retest reliability, convergent validity, known-groups validity and sensitivity to change (responsiveness) using anchor- and distribution-based methods.

6.20.1.2.5.1. Internal Consistency

Internal consistency reliability addresses the extent to which individual items in the instrument measure a common underlying concept by examining the item-item or item-total, correlations for the GPSS using Cronbach’s coefficient alpha (Cronbach 1951).

The values are presented descriptively on an interval level scale from 0 to 1.0, with higher scores indicating a more reliable (homogeneous) instrument. Cronbach’s alpha coefficients between 0.7 and 0.9 will indicate good internal consistency, values between 0.4 and <0.7 will indicate moderate internal consistency, and values <0.4 will indicate low internal consistency reliability (Nunnally and Bernstein 1994, Cronbach 1951). Cronbach’s alphas greater than 0.70 are generally considered acceptable for group comparisons (Hays and Revicki 2005). Internal consistency reliability will be assessed for the GPSS at the day prior to the first study drug injection and again at the day prior to the Week 12 injection based on item-level data. Cronbach’s alpha for the GPSS total score and a summary of Cronbach’s alpha levels with each constituent item deleted will also be reported.

Pearson and Spearman correlations will be used to calculate inter-item correlations for GPSS items. These correlations examine the extent to which items within the measure related to each other. These correlations will be used to confirm that the measures are performing in this sample as expected. Items will be flagged as being potentially redundant/overlapping when the item-item correlation is greater than 0.80.

6.20.1.2.5.2. Test-Retest Reliability

Test-retest reliability has been emphasized by the FDA as an important aspect of reliability in the FDA PRO Guidance (FDA 2009). Test-retest reliability reflects the ability of the instrument to give reproducible results when the clinical state is stable and indicates the degree to which a measure produces consistent results over several administrations. Test-retest reliability will be examined for: 1) GPSS items and total score, 2) GPSIS subscales, 3) SFQ item 2, and 4) sPGA of Genitalia prior to the first study drug injection. Stable subjects will be defined in two ways: 1) patients who had the same rating on the overall sPGA at screening and baseline visit, and 2) patients whose change in mGPASI score at screening and baseline visit <0.5 SD of mGPASI at baseline. For daily diary, patients are required to enter start entering GPSS at least 14 days prior to the first injection. The test score will be the average of 8 to 14 days prior to the first injection; whereas the re-test score will be the average of 1 to 7 days prior to the first injection, the same as baseline score. When there are less than 4 non-missing assessments within respective window, the search window will be expanded repeatedly until 4 non-missing assessments are available to compute the average score. Otherwise, the test, or re-test score will be set to missing. For weekly diaries, including GPSIS and SFQ, patients are also required to have 2 assessments collected prior to the first study drug injection in order to be included in the analysis.

Test-retest reliability will be assessed using intra-class correlations coefficients (ICCs) and paired sample t-tests among stable patients only.

Intra-class correlations coefficients range from 0 to 1.0, with higher scores indicating a more stable instrument. The hypothesis is that there will be no significant differences in scale scores when there is no change in disease status. Given that the majority of evaluated measures are single-item scales, a threshold of >0.60 will be supportive of test-retest based on the lower limit provided by Devellis (1991).

6.20.1.2.5.3. Construct Validity

6.20.1.2.5.3.1. Convergent and Divergent Validity

Construct validity is the degree to which a measure is related to other measures or constructed in a manner that is consistent with theory. *Convergent validity* involves demonstrating that different measures of the same concept substantially correlate, while *divergent validity* demonstrates that concepts that are supposed to be unrelated are, in fact, unrelated. The relationship between the 1) GPSS items and total score, 2) GPSIS subscales, 3) SFQ item 2, and 4) sPGA of Genitalia, and the DLQI domains, SF-36 scores, and mGPASI will be examined using Pearson, Spearman rank correlations, and polychoric correlation as appropriate.

Convergent validity of the scales of interest will be demonstrated at baseline and Week 12 by moderate to high correlations between the measures, except where noted. Moderate to high correlations ($\geq .30$) demonstrating convergent validity (Cohen 1988) are expected for:

1. GPSS individual item and total scores and
 - a. DLQI symptoms and feelings domain score, personal relationship score and total score

- b. SF-36 PCS scores
 - c. mGPASI score
 - d. PatGA-Genital
2. GPSIS subscales and
 - a. DLQI personal relationships domain score
 - b. DLQI sexual difficulties item
 - c. PatGA-Genital
 3. SFQ item 2 and
 - a. DLQI personal relationships domain score
 - b. DLQI sexual difficulties item
 - c. PatGA-Genital
 4. sPGA of Genitalia
 - a. DLQI symptoms and feelings domain score
 - b. mGPASI
 - c. PatGA-Genital

Divergent validity of the scale of interest will be assessed at baseline, and Week 12. Pearson, Spearman's rank correlation and polychoric correlation will be calculated between 1) GPSS individual items and total score, 2) GPSIS subscales, 3) SFQ item 2, and 4) sPGA of Genitalia, and the SF-36 mental health, role physical and role emotional scores, and the DLQI daily activities, leisure, and work and school domain scores. Small correlations (demonstrating discriminant validity) are anticipated for each of these comparisons (correlations < 0.30; Cohen 1988).

6.20.1.2.5.3.2. Known-Groups Validity

Known-group validity is the extent to which scores from an instrument are different for groups of participants that differ on a relevant clinical or other indicator. Determining known-group validity involves evaluating an instrument in relation to clinical measures of disease status (Stewart et al. 1992; Hays and Revicki 2005). Known-groups validity will be assessed at baseline and Week 12 for: 1) GPSS individual items and total score, 2) GPSIS subscales, 3) SFQ item 2, and 4) sPGA of Genitalia by disease severity. Groups will be defined using several different criteria: 1) using DLQI score categories (score categories: 2-10, 11-20, 21-30); and 2) using PatGA-Genitalia scores (score categories: 0-1, 2-3, 4-5). Additionally, for exploratory purposes, known-groups validity of the SFQ item 2 will be assessed at baseline-and Week 12 using the DLQI sexual difficulties item to define subgroups of patients. Mean scores on the individual items/subscale/total score will be compared for each subgroup using ANCOVA at baseline, and Week 12 controlling for age, sex, and baseline BSA (<10% vs ≥10%).

When the sample size in a subgroup is less than 10% of the analysis population, the subgroup will be repeatedly collapsed with the adjunct subgroups until the sample size in the collapsed subgroup is greater than 10% of the analysis population.

6.20.1.2.5.4. Responsiveness

Responsiveness refers to the extent to which the instrument can detect changes in patients known to have changed in clinical status (Hays and Revicki 2005). The responsiveness of the 1) GPSS item and total score, 2) GPSS subscales, 3) SFQ Item #2, and 4) sPGA of Genitalia will be determined by comparing changes in item/total scores with the changes in selected clinical and health status measures.

The following variables and time points will be used for these analyses:

- **PatGA-Genitalia:** The change scores of the GPSS item and total score from baseline to Week 12 will be correlated with changes in the PatGA-Genitalia at these time points. The change scores of the individual items and GPSS total score from baseline to Week 12 will also be examined using PatGA-Genitalia as an anchor. The means of GPSS and sPGA of Genitalia scores will be compared for patients reporting ≥ 1 point PatGA-Genitalia Improvement, no change, or ≥ 1 worsening in PatGA-Genitalia using ANCOVA adjusted for age, sex, genital psoriasis duration and baseline scores.
- **mGPASI:** The change scores of the GPSS individual item and total score from baseline to Week 12 will be correlated with changes in the mGPASI at these time points. For exploratory purposes, the change scores of the GPSS individual item and total score from baseline to Week 12 will also be examined for mGPASI defined groups using ANCOVA. Groups will be defined as patients who experienced improvement on the mGPASI of ≥ 0.5 SD versus improvement < 0.5 SD.

Additionally, for exploratory purposes, responsiveness of the subscale of GPSIS, Sexual Activity Avoidance Subscale, and sPGA of Genitalia will be assessed using the Week 12 score. Both scales at Week 12 will be anchored on PatGA-Genitalia and mGPASI defined previously.

6.20.1.2.5.5. Clinical Significance

To ensure proper interpretation of the data, it is useful to develop evidence for clinical significance of score changes. The lower end of a range of clinical significance can be termed the responder definition (RD), which is defined as “the individual patient PRO score change over a predetermined time period that should be interpreted as a treatment benefit” (FDA 2009). In the absence of a single, unequivocal indicator of change, a number of analytic methods will be used to assess the RD of the GPSS individual item and total score, GPSIS, and SFQ. The results of these analyses can be used to guide score interpretation. Both anchor-based methods and distribution-based methods will be used for determining RD. However, anchor-based methods are preferred by the FDA for interpretation of PRO scores (FDA 2009) and will be considered the primary analysis. Distribution-based methods will be considered supportive and secondary (Revicki et al. 2008).

6.20.1.2.5.5.1. Anchor-Based Method

PatGA-Genitalia will be used as an anchor to determine the RD of each measure, including GPSS item and total score, GPSIS subscale, and sPGA of Genitalia. The RD will be estimated as the mean change scores of patients who improved by one and two points on the PatGA-Genitalia from baseline to Week 12. Effect size (ES) statistics will then be calculated for each group of patients as the mean difference between the baseline and Week 12 visit scores divided by the standard deviation of the baseline domain scores of each measure (Cohen 1988). The following cutoff values will be used to interpret effect size: small ES = 0.2, moderate ES = 0.5, and large ES = 0.8.

Additionally, the RD of the change in GPSS item and total score and the subscale of GPSIS, Sexual Activity Avoidance Subscale, from baseline to Week 12 will be derived by anchoring them on sPGA of Genitalia (0,1) at Week 12. The correlation between change in each measure and change in sPGA of Genitalia from baseline to Week 12 will first be computed to assess the strength of the anchor. A logistic model will then be utilized by regressing the change in each measure on the anchor. Concordance index will be computed to assess the adequacy of the model fitting. Predictive statistics, including sensitivity, specificity, positive predictive value, negative predictive value and Youden index, will be presented at each possible change of value for each measure.

A RD will be derived for sPGA of Genitalia and the subscale of GPSIS, Sexual Activity Avoidance Subscale at Week 12 by anchoring on 1) PatGA-Genitalia (0,1) at Week 12 as an anchor. Correlation between each measure and anchor variable will be first assessed prior to constructing the logistic model.

A RD will be derived for SFQ Item #2 and GPSIS subscales comprising the change of score and static score at Week 12 using PatGA-Genital (0,1) and sPGA of Genitalia (0,1) at Week 12 as anchors.

6.20.1.2.5.5.2. Distribution-Based Method

For the distribution-based methods, supportive evidence for the RD will be assessed using one standard error of measurement (SEM) and 0.5 SD of the scales of interest at baseline.

Standard of error of measurement has been proposed as a useful distribution-based statistic for evaluating clinically meaningful change in health-related quality of life (HRQL) measures (Wyrwich et al. 1999a; Wyrwich et al. 1999b). The SEM describes the error associated with the measure and is estimated by the baseline standard deviation of the measure multiplied by the square root of one minus its reliability coefficient (ICC from the test-retest assessment).

Previous research suggests that one SEM is roughly associated with a clinically important difference for PRO measures (Wyrwich et al. 1999a; Guyatt et al. 2002). Other research suggests changes (or differences) of 0.20 to 0.30 effect size may be indicative of a minimal important difference (Osoba and King 2005; Revicki et al. 2008).

An alternative distribution-based approach consists of calculating a 0.5 SD of the scales of interest at baseline. It has been suggested that one-half of a standard deviation of a measure

represents a clinically meaningful change, while a change corresponding to 0.2 of a standard deviation of measure is a small effect (Norman and Streiner 2003). The 0.5 SD estimate can be considered to provide an upper boundary for what would constitute a meaningful change, while 0.2 provides a lower boundary (Revicki et al. 2008). Given that a clinically important change is of interest, a 0.5 SD will be used, with 0.2 SD calculated to provide reference for range.

The number and percentage of patients meeting the various RDs derived from anchor- and distribution-based methods for each measure will also be calculated-

Using the results from both the anchor- and distribution-based approaches, triangulation across possible thresholds indicating a minimal but meaningful change will be considered, and a reasonable RD will be selected (Leidy and Wyrwich 2005).

6.20.1.2.5.5.3. Cumulative Distribution Functions

Cumulative distribution function (CDF) shows the proportion of the population scoring less than or equal to each possible change score. Cumulative distribution functions are useful in that they graphically characterize the treatment effect or differences between groups. Cumulative distribution functions will be constructed for changes from baseline to Week 12 in GPSS individual items and total scores, and sPGA of Genitalia scores stratified by treatment and by responder status defined by PatGA-Genitalia. For all CDF plots, the x-axis is the score change from baseline to final visit for each measure. The y-axis is the cumulative proportion of the patients in each of the corresponding categories that reach the score change on the x-axis.

Another CDF will be presented for the subscale of GPSIS subscales and sPGA of Genitalia score at Week 12 stratified by treatment groups.

7. Unblinding Plan

A separate document will describe the blinding and unblinding plan.

8. References

- [APA] American Psychiatry Association. Diagnostic and Statistical Manual of Mental Disorders. 4th ed. Washington DC: American Psychiatric Association; 1994.
- Cohen J. *Statistical Power Analysis for the Behavioral Sciences*. Hillsdale, NJ: Lawrence Erlbaum Associates Inc; 1988.
- Cronbach LJ. Coefficient alpha and the internal structure of tests. *Psychometrika*. 1951;16(3):297-334.
